#### 6.4.3 Analysis of Primary Outcome of Interest

This validity of the IMPACT in measuring QOL will be determined by calculating Pearson's r between the score from each IMPACT module and subscale with the 15D QOL survey.

---

---

Each module or subscale will be considered valid if it shows significant ( $p < 0.05$ ) and at least moderately-positive correlation ( $r > 0.4$ ) with the 15D. All independent variables that influence IMPACT scores will be controlled for in a multivariable regression model.

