## **2 STUDY OBJECTIVES**

### **2.1 Primary Objective**

The primary objective of this study is to determine the validity of each IMPACT module and subscale for measuring QOL in patients with maxillofacial trauma.

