#### **3.2.2 Total Number of Study Sites/Total Number of Subjects Projected**

The study will be conducted at approximately 10 investigative sites across the United States. Recruitment will stop when 150 subjects have completed each IMPACT Module. It is expected that approximately 500 subjects will be enrolled to yield 150 subjects that are indicated for each IMPACT module.

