## 5 STUDY EVALUATIONS AND MEASUREMENTS

### 5.1 Screening and Monitoring Evaluations and Measurements

#### 5.1.1 IMPACT Survey

The IMPACT is a PROM with 4 independent modules. The first is a “General Module” for all patients with maxillofacial trauma. The remaining three modules were designed for specific fractures involving nasal, orbital, and/or jaw regions (Table 1). Each module takes 2-5 minutes to complete for a total of 2-20 minutes/survey depending on fracture pattern.

1. General Module (IMPACT-G)
  - a. **Target patients:** All maxillofacial trauma patients
  - b. **Number of questions:** 21
  - c. **Structure:** 5-point Likert Scales (except for a single “pain score” from 0-10)
  - d. **Subscales (4):** Overall Facial Appearance, Psychosocial Function, General Symptoms, Pain
2. Nasal Module (IMPACT-N)
  - a. **Target patients:** Fractures of the nasal bones and/or sinuses
  - b. **Number of questions:** 15
  - c. **Structure:** 5-point Likert Scales
  - d. **Subscales (2):** Nasal Function, Nasal Appearance
3. Orbital Module (IMPACT-O)
  - a. **Target patients:** Fractures of the orbital walls or rim
  - b. **Number of questions:** 15
  - c. **Structure:** 5-point Likert Scales
  - d. **Subscales (2):** Orbital Function, Orbital Appearance
4. Jaw Module (IMPACT-J)
  - a. **Target patients:** Fractures of the mandible or upper jaw
  - b. **Number of questions:** 20
  - c. **Structure:** 5-point Likert Scales
  - d. **Subscales (2):** Jaw Function, Jaw Appearance

**Table 1:** User guide for the Integrated Modular Patient-Reported Outcome Assessment for Craniomaxillofacial Trauma (IMPACT).

IMPACT Modules	IMPACT-G	IMPACT-N	IMPACT-O	IMPACT-J
Facial Soft Tissue Injury	X			
Upper Facial Third Fractures				
Frontal Sinus	X	X		
Superior orbital rim	X		X	
Middle Facial Third Fractures				
Nasal bones and/or septum	X			
Facial sinus fractures	X	X		
Naso-orbito-ethmoid	X	X	X	
Orbital rim and/or wall	X		X	
Zygomaticomaxillary complex (ZMC)	X		X	X
Zygomatic arch fracture	X			X
Upper dentoalveolar or palate	X			X
Le Fort I	X	X		X
Le Fort II/III	X	X	X	X
Lower Facial Third Fractures				
Mandible	X			X
Lower dentoalveolar	X			X

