### 5.1.2 15D Survey

The 15D is a well-established survey to assess QOL over numerous medical and/or surgical patients. It has 15 questions each on unique 5-point Likert scale and all related to some QOL theme. This survey has previously been used in maxillofacial trauma. It was chosen as a control for this study given its robust validity for measuring QOL and several individual themes that are specifically related to maxillofacial trauma such as eating, drinking, speech, anxiety, and depression.

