#### 6.4.2 PROM Scoring

- IMPACT Scoring: IMPACT modules consist of 8-16 Likert scale questions from 0-4 (5-point). The total module score will be standardized by taking the average of all questions in a module then multiplying x25, giving a total module score of 0-100 with higher scores indicating more worse QOL impairment. The pain scale will be reported separately and the final score will be the patients pain score from 0-10 multiplied by 10 for a final pain score of 0-100. For the initial analysis, partially completed surveys with any number of missing answers will be included. Individual subscales for each module will also be given a “subtotal” score which is the average of the Likert scale answers in that subscale, multiplied by 25 for a standardized score from 0-100.
- 15D Scoring: The 15D is scored using a non-linear, copyright algorithm that accounts for baseline demograpic variability. It is available here: <https://15d-instrument.net/15d/> (15D©/Harri Sintonen). The code for this analysis already been released to the host institution for use in the analysis of this study.

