#### **6.5 Sample Size and Power**

For PROM development, 4-10 participants per item with an absolute minimum of 100 is often recommended for field testing. Therefore, this study will have 150 patients complete each module. Based on a host institution pilot study of 50 patients, the percentage of those being indicated for the IMPACT-N, IMPACT-O, and IMPACT-J were 40%, 30%, and 60%, respectively. Therefore, it is expected that 500 patients with maxillofacial trauma will need to be recruited in order to properly validate the least common IMPACT-O with at least 150 patients. The anticipated nonresponse rate from this pilot study was 33%, so it is expected that a total of 750 patients will need to be invited in order to meet this sample size.

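### The primary validity rule requires a positive r above 0.4 with the 15D, but IMPACT is scored worse-upward, the 15D direction is not stated and neither score is reversed

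*Protocol*

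**What the plan says.** The primary objective (Protocol 2.1) is to "determine the validity of each IMPACT module and subscale for measuring QOL". Section 6.4.3 makes this a decision rule on Pearson's r between each IMPACT score and the 15D. A score is valid if p < 0.05 and it shows "at least moderately-positive correlation ( $r > 0.4$ ) with the 15D". The positive sign is set twice, in words and by the inequality.

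Section 6.4.2 gives the IMPACT direction: "giving a total module score of 0-100 with higher scores indicating more worse QOL impairment". Subscale scores average the same Likert answers and multiply by 25, with no reversal mentioned, so they run the same way. The 0-10 pain item is multiplied by 10 and reported separately, and its direction is not stated.

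For the 15D, section 6.4.2 describes only the type of scoring: "The 15D is scored using a non-linear, copyright algorithm". Section 5.1.2 says it was chosen "given its robust validity for measuring QOL". Neither section says whether a high 15D score is good or bad. The abstract and sections 6.1 and 6.4.3 describe the correlation without reversing a score, taking an absolute value or naming an expected sign.

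**The concern.** A signed threshold has meaning only when both scores have a known direction. Here one direction is given (IMPACT, worse-upward) and the other is not. That the 15D measures quality of life does not settle the matter, because section 2.1 says the same of IMPACT, which runs worse-upward.

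If higher 15D means better quality of life, the rule is inverted. A module that tracks impairment well gives a strongly negative r and is declared not valid. A module would pass only if worse IMPACT scores went with better quality of life.

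This is the only decision rule for the primary objective. If the sign were changed after negative correlations had been seen, the primary criterion would have been altered post hoc, even if the change were sensible.

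**Working it through.** **Inputs from the protocol**

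- Threshold r > 0.4, p < 0.05 (6.4.3).
- 150 completers per module, about 500 enrolled (3.2.2, 6.5).
- Module shares from the pilot (6.5): "the percentage of those being indicated for the IMPACT-N, IMPACT-O, and IMPACT-J were 40%, 30%, and 60%, respectively".
- IMPACT-G target group (5.1.1): "All maxillofacial trauma patients".
- Subscales (5.1.1): G 4, N 2, O 2, J 2.

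**Assumptions, not in the protocol**

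- Higher 15D = better quality of life.
- True correlation between -0.4 and -0.6; the protocol gives no expected r.

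**The plan's own figures.** Enrolment: 150 / 0.30 = 500, as stated. Invitations: 500 / (1 - 0.33) = 747, in line with the stated 750 (exactly 750 if nonresponse is one third). The protocol gives no power figure for the r > 0.4 rule, so there is none to reproduce.

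**Scores covered.** 4 modules + (4 + 2 + 2 + 2) subscales = 14.

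**Expected n from 500 enrolled.** O: 0.30 × 500 = 150. N: 0.40 × 500 = 200. J: 0.60 × 500 = 300. G: 500.

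**Which condition decides.** At n = 150 the smallest |r| with two-sided p < 0.05 is t / sqrt(n - 2 + t²) = 0.160. The significance condition does not bind, so the signed 0.4 threshold decides.

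**Probability of being declared valid.** By the Fisher z approximation, SE = 1/sqrt(n - 3) and P(r > 0.4) = 1 - Φ[(atanh 0.4 - atanh ρ) / SE]. Here atanh 0.4 = 0.4236, and at n = 150 SE = 1/sqrt(147) = 0.0825.

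- As written, ρ = -0.4: (0.4236 + 0.4236) / 0.0825 = 10.3 SE, so P is about 0. At -0.5 and -0.6 the threshold is further away still.
- Sign aligned, |ρ| = 0.4: the threshold equals the true value, so P = 0.50.
- Sign aligned, |ρ| = 0.5: (0.5493 - 0.4236) / 0.0825 = 1.52 SE, so P = 0.936.
- Sign aligned, |ρ| = 0.6: (0.6931 - 0.4236) / 0.0825 = 3.27 SE, so P = 0.9995.

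**Other modules, true ρ = -0.5**

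| Module | n | SE | As written | Sign aligned |
|---|---|---|---|---|
| O | 150 | 0.0825 | 0.000 | 0.936 |
| N | 200 | 0.0712 | 0.000 | 0.961 |
| J | 300 | 0.0580 | 0.000 | 0.985 |
| G | 500 | 0.0449 | 0.000 | 0.9975 |

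**Simulation check.** With 20,000 bivariate normal samples of 150 at ρ = -0.5, -0.6 and -0.7, none passed the rule as written. With the sign aligned, 0.941, 0.999 and 1.000 passed.

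**Other branch.** If higher 15D means worse quality of life, the true correlations are positive, the aligned column applies to the rule as written, and nothing is lost.

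**The case against.** The strongest objection is that the harm depends on a fact the protocol does not give. From the document alone one can show an unstated direction, but not a wrong rule. This stands, and it is why the size is given conditionally.

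Second, the 15D is bound to a named algorithm whose code the host institution already holds, so its orientation is fixed before any data exist, and a later sign correction could be called clerical. That is partly right: the direction is knowable now. But a fixed algorithm does not align its output with a worse-upward IMPACT score. A correction made after the correlations have been seen is also harder to defend than one made beforehand.

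Third, aligning scores may be left to the statistical analysis plan, which is not at hand. That would answer a silent protocol. This one states the criterion. A plan using r < -0.4 would contradict section 6.4.3, and one using r > 0.4 would repeat the problem unless it reversed a score when the directions are opposite.

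Fourth, the positive wording may have meant strength of association. That is plausible as intent, but the literal inequality excludes every negative r.

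Finally, the probabilities use an unadjusted r and assumed correlations, whereas sections 6.1 and 6.4.3 also call for control of predictors. Accepted: the figures show the scale of the effect and do not predict the trial's results. Reading a higher pain score as more pain is also natural, so that gap is minor.

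**Conclusion.** The concern holds and should be resolved before analysis. The primary criterion requires a positive correlation between a worse-upward score and a score of unstated direction, with no reversal and no absolute value. That is a defect whichever way the 15D runs.

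Its consequence depends on the direction. If higher 15D means better quality of life, the rule would almost never declare a sound module valid, whereas an aligned rule at n = 150 would do so with probability 0.50 to 0.9995 over the assumed range of |r| from 0.4 to 0.6. If the 15D runs worse-upward, the rule works as written. The document does not show which case applies, so confidence in the practical harm is medium; confidence that the text needs correcting is higher.

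**What to change.** In section 6.4.2, state whether a higher 15D score means better or worse quality of life, and state the direction of the pain score. Then amend section 6.4.3 in one of two ways:

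1. Prespecify the expected sign and require |r| > 0.4 in that direction, which is r < -0.4 if higher 15D means better.
2. Only if the stated directions are opposite, reverse one score before correlating (for example, 100 minus IMPACT) and keep r > 0.4.

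Make the change before any correlation is computed. It costs one or two sentences in each section. The host institution holds the 15D scoring code and can confirm the direction at once. Sample size, data collection and participants are unaffected.

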## 6 STATISTICAL CONSIDERATIONS

### 6.1 Primary Endpoint

The primary endpoint pertains to the primary objective, determining the validity of each IMPACT module and subscale for measuring QOL in patients with maxillofacial trauma. This will be determined by correlating the IMPACT scores with the corresponding 15D score, controlling for any independent predictors of IMPACT and 15D scores.

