#### 6.4.1 Baseline Data

The following chart review variables will be abstracted after informed consent is obtained and the initial survey is completed. This data will be summarized descriptively with average, median, range, interquartile range, and standard deviation, as appropriate. Each variable will then be tested for association with IMPACT scores on univariable analysis. Clinically or statistically significant variables will then be included in subsequent multivariable testing.

---

---

- Sociodemographic data: Age, sex, race, ethnicity, marital status, smoking status, payor type (private, medicare, Medicaid, government, none / self-pay, or other), and Social vulnerability index (SVI) values based on home address.
  - SVI: A measure of social vulnerability assigned to each zip code or census tract by the Center for Disease Control and Prevention.
- Trauma data: Mechanism, concomitant multisystem trauma, airway status, level of care (discharged from emergencet room, floor/stepdown admit, intensive care admit), presenting signs or symptoms (cranial nerve weakness, trismus, malocclusion, visual impairment), description of facial trauma, comprehensive facial injury (CFI) score, and Facial Injury Severity Score (FISS).
  - CFI: An objective scale based on maxillofacial imaging and clinical exam providing an integer that represents fracture severity by correlating it with the operative time for repairing each fracture.
  - FISS: An objective scale based on maxillofacial imaging and clinical exam providing an interger that represents the objective severity of facial trauma by correlation with the cost of management.
- Management data: Treatment (observation, bedside intervention, or surgical repair), type of surgical repair (closed reduction, open reduction, internal fixation, external fixation, and maxillomandibular fixation [MMF]), hospital length of stay (days), disposition (home versus medical facility)
- Objective complications: Wound infection or dehiscence, Malunion or nonunion, hardware extrusion, or any unplanned return to the emergency department, admission or reoperation related to the facial injury.
- Survey metadata: time from trauma to survey (days), time from intervention to survey (if applicable; days), presence of maxillomandibular fixation at the time of the survey.

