#### **6.4.4 Analysis of Secondary Outcomes of Interest**

1. IMPACT independent predictors: This secondary objective will identify independent variables that are associated with IMPACT scores. Multivariable logistic and linear regression models will be developed for categorical and continuous independent variables, respectively, and tested for association with each IMPACT score. Those independently associated with the IMPACT will be reported and factored into the multivariable regression for the primary endpoint.
2. Internal consistency and reliability will be measured by Cronbach alpha testing, item-response theory (IRT), and correlation between initial and followup surveys for patients completing both within one month.
3. The MCID for each module and subscale will be calculated using an anchor-based approach with a single item that addresses each patient's overall satisfaction.

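### The variables to be controlled for in the IMPACT–15D validity correlation can include causes of the impairment both scales should register, so the adjusted coefficient can understate validity and, if the 0.4 rule is applied to it, a valid module can fail

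*Protocol*

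**What the plan says.** Protocol section 6.1 defines the primary endpoint as an adjusted correlation: "This will be determined by correlating the IMPACT scores with the corresponding 15D score, controlling for any independent predictors of IMPACT and 15D scores".

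Section 6.4.3 describes the analysis as "calculating Pearson's r between the score from each IMPACT module and subscale with the 15D QOL survey". It requires p < 0.05 "and at least moderately-positive correlation", set at r > 0.4, and then adds a separate sentence: "All independent variables that influence IMPACT scores will be controlled for in a multivariable regression model".

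Two other places say how the control set is built. Section 6.4.1 tests each chart-review variable against IMPACT and states: "Clinically or statistically significant variables will then be included in subsequent multivariable testing". Section 6.4.4 item 1 passes the result on to the primary analysis: "Those independently associated with the IMPACT will be reported and factored into the multivariable regression for the primary endpoint".

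The candidates in section 6.4.1 include the CFI and FISS severity scores, the description of the facial trauma, "presenting signs or symptoms (cranial nerve weakness, trismus, malocclusion, visual impairment", the type of treatment, and objective complications. No section sets aside variables that belong to what IMPACT is meant to measure. Section 6.3 looks for confounding by the same test, correlation with IMPACT.

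**The concern.** A validity coefficient asks whether two scales rise and fall together because they register the same thing. In this population, part of that common movement should come from the injury and its consequences. The second part of the protocol's own objectives (section 2.2, item 1) treats injury and treatment variables as possible influences on QOL. IMPACT has Jaw Function and Orbital Function subscales (section 5.1.1), which would be expected to respond to trismus, malocclusion or visual impairment. Section 5.1.2 says the 15D was chosen partly because some of its themes relate to facial trauma.

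If a variable drives both scores, holding it fixed removes agreement that is evidence of validity. The selection rule can work against the instrument: the more closely a module follows the injury, the more injury variables qualify for control.

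At stake is the primary conclusion for each module and subscale. If the 0.4 rule is read on the adjusted coefficient, a module that meets it on the raw correlation can be declared not valid. If it is read on the raw correlation, the adjusted result may disagree for a reason that has nothing to do with the quality of the scale.

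**Working it through.** **Inputs from the protocol.** Threshold r > 0.4 with p < 0.05 (section 6.4.3); 150 patients per module (section 6.5).

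**The plan's own figures.** Section 6.5 reaches 500 recruited and 750 invited: 150/0.30 = 500, and 500/(1 − 1/3) = 750 (747 with exactly 33%). These reproduce and are not affected by this point. The protocol gives no expected r and no power for the 0.4 rule.

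**Assumptions.** The documents give no correlation between IMPACT and the 15D, or between either score and the chart variables. I treat the controlled variables as one composite with correlation a with IMPACT and b with the 15D, take a raw r of 0.50, and orient the scores so that agreement is positive.

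**Step 1: adjusted r.** Partial r = (r − ab) / √[(1 − a²)(1 − b²)]. With a = b = c this becomes (r − c²)/(1 − c²). For c = 0.5: (0.50 − 0.25)/(1 − 0.25) = 0.33.

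**Step 2: chance of an observed r above 0.4.** Fisher's z has standard error 1/√(n − 3), or 1/√(n − 4) with one controlled composite. At n = 150 any r above about 0.16 is significant at two-sided 5%, so the size condition decides.

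- Unadjusted, true 0.50: (0.549 − 0.424) × √147 ≈ 1.52, giving about 94%.
- c = 0.5, true 0.33: (0.347 − 0.424) × √146 ≈ −0.93, giving about 18% (simulation of 20,000 trials: 18%).

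| c (both scores) | adjusted r | chance of observed r > 0.4 |
|---|---|---|
| none controlled | 0.50 | 94% |
| 0.2 | 0.48 | 88% |
| 0.3 | 0.45 | 77% |
| 0.4 | 0.405 | 53% |
| 0.5 | 0.33 | 18% |
| 0.6 | 0.22 | about 1% |

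**Step 3: where the adjusted r crosses 0.4.** Setting (r − c²)/(1 − c²) = 0.4 gives c = √[(r − 0.4)/0.6]: 0.29 for a raw r of 0.45, 0.41 for 0.50, 0.50 for 0.55, 0.58 for 0.60 and 0.71 for 0.70.

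**Step 4: unequal correlations.** With a = 0.4 and b = 0.2: (0.50 − 0.08)/√(0.84 × 0.96) = 0.47, and the chance of passing is about 84%. With r = 0.50 and a = 0.5, the adjusted r is 0.58, 0.52, 0.47, 0.42, 0.38 and 0.33 for b = 0, 0.1, 0.2, 0.3, 0.4 and 0.5. So the loss needs correlation with both scores, and with b near zero the coefficient rises.

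**The case against.** Five things can be said for the plan.

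- **The threshold may apply to the raw r.** Section 6.4.3 attaches 0.4 to Pearson's r, the abstract names Pearson's r for criterion validity, and the regression sentence carries no threshold. On that reading no module fails through adjustment. This stands as an ambiguity, but it does not clear the plan: section 6.1 builds the control into the primary endpoint, and section 6.4.4 item 1 sends the predictors into the primary-endpoint model.
- **The listed variables are only candidates.** Only those independently associated with IMPACT enter, and which ones will do so is unknown. This stands.
- **The links to the 15D may be weak.** The protocol relates CFI to operative time and FISS to management cost, surveys may come up to a year after injury, and section 1.2 says parts of the patient experience cannot be seen from imaging or chart review. This stands as a reason to expect a smaller loss than the lower rows of the table.
- **Adjustment does not always pull the coefficient towards zero.** A reader might infer that it does. Step 4 shows otherwise, so the documents do not support that inference.
- **Agreement among similarly injured patients is a legitimate, stricter question.** It checks that the correlation is not merely a product of mixing minor and severe injuries. That is a fair companion analysis, but it is poorly suited to be the criterion for validity.

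**Conclusion.** The point holds in a conditional form. The protocol ties its primary validity analysis to control for every variable found to predict IMPACT, and the candidates include variables that can be causes of the impairment both scales should register. Where such variables are selected and correlate with both scores, the adjusted r understates validity.

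The size is unknown. For an assumed raw r of 0.50 the effect is slight at a shared correlation of 0.2 to 0.3, borderline at 0.4, and takes the true adjusted value below the threshold from about 0.41 upwards. The fall in the chance of passing from about 94% to about 18% needs a correlation of 0.5 with both scores, a value that nothing in the documents supports or excludes.

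A reader might conclude that the plan will reject valid modules. The documents do not support that: it requires the 0.4 rule to be applied to the adjusted coefficient, which section 6.1 implies and section 6.4.3 leaves open, as well as sufficient correlation with the 15D. The supportable statement is that a valid module can fail. It should be corrected before results are seen.

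**What to change.** - In sections 6.1 and 6.4.3, state that the validity criterion, both size and p-value, applies to the unadjusted Pearson's r, reported with its 95% CI.
- In sections 6.1, 6.4.3 and 6.4.4 item 1, remove facial-injury severity (CFI, FISS, fracture description), presenting signs, treatment and complications from the variables controlled for in the validity analysis.
- Use the association of those variables with IMPACT, already planned in section 6.4.1, as known-groups evidence.
- Report any adjusted correlation only as a sensitivity analysis, limited to prespecified variables outside the construct, such as age and sex. Other candidates, such as multisystem trauma, level of care, length of stay and time since trauma, should be classified in advance on the same principle and not admitted because they correlate with IMPACT.

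The cost is a change of wording in the protocol and any SAP. It needs no new data and no change to the sample size.
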